6.7.2.3 Dosing Modification for Specific Adverse Events With GEN1053 or IM

Thrombocytopenia Related to GEN1053

The following guidelines should be followed for GEN1053-related thrombocytopenia:

- If thrombocytopenia ≥ grade 2 is identified, with or without bleeding, further treatment must be interrupted.
- If grade ≥ 2 thrombocytopenia fails to resolve to grade ≤1 within 21 days after the planned dosing date, the subject is to discontinue trial treatment unless approved otherwise by the sponsor. Per protocol, observation procedures and assessments will continue until the subject withdraws from the trial or starts another course of systemic anticancer therapy.
- Retreatment may be considered if thrombocytopenia resolves to grade ≤1 within 21 days after the planned dosing date. The sponsor and investigator will discuss any safety concerns in order to decide whether the next cycle should be administered at the same schedule or whether the dosing interval in subsequent cycles should be increased.
- If the retreatment results in grade ≥2 thrombocytopenia, the next administration of trial treatment should be delayed for up to 21 days until the toxicity has resolved to grade ≤1. The sponsor and investigator will discuss any safety concerns in order to decide whether next cycle should be administered at the same schedule or whether the dosing interval in subsequent cycles should be increased.
- If more than 2 dose interruptions occur due to grade ≥2 thrombocytopenia, trial treatment will be discontinued. Per protocol, observation procedures and assessments will continue until the subject withdraws from the trial or starts another course of systemic anticancer therapy.
- Trial treatment must be prematurely discontinued if the subject experiences grade 4 thrombocytopenia or grade 3 thrombocytopenia with bleeding. For subjects with platelet count <50×10⁹/L, aspirin or other concomitant medications with effect on platelet function or coagulation should be paused. For subjects with severe, persistent thrombocytopenia potentially related to GEN1053, it is recommended to perform a bone marrow biopsy.

Bleeding:

Subjects with any bleeding symptoms, even mild, (eg, unjustified bruising, purpura, petechiae, epistaxis or gingival bleeding) will be instructed to contact the site immediately. Lab tests must be drawn to assess hematological parameters including platelets in case of signs of bleeding. Importantly, \geq grade 3 thrombocytopenia and \geq grade 2 bleeding events need to be reported within 24 hours irrespective of event seriousness (see Section 8.4.3).

• For any clinically significant bleeding event, supportive care may be provided following local guidelines. For significant bleeding associated with thrombocytopenia of ≥ grade 2, platelet transfusions, high-dose corticosteroids or immunoglobulin therapy should be considered according to local standards.

Neutropenia and Febrile Neutropenia Associated With GEN1053 or IM Administration

Table 6-4Dosing Modification and Management of Neutropenia and Febrile
Neutropenia

CTCAE Term	Toxicity Grade (CTCAE v5.0)	Dose Modification	Guidance for Management of AE
Neutropenia	Grade 3 or Grade 4	Withhold treatment until	Administer colony-stimulating factors including
or		resolution to \leq grade 1	G-CSF, pegylated G-CSF, or GM-CSF according to
Febrile			Institutional standards.
neutropenia			For grade 3 or 4 neutropenia occurring in Cycle 1,
			grade 3 or 4 neutrophil count must be observed in
			2 consecutive assessments at least 12 hours apart
			without improvement prior to administration of growth
			factors.

AE=adverse event; CTCAE=Common Terminology Criteria for Adverse Events; G-CSF=granulocyte colony-stimulating factor; GM-CSF=granulocyte/macrophage colony-stimulating factor.

Cytokine Release Syndrome Related to GEN1053 or IM

In the unexpected case an event of CRS occurs, grading of the CRS should be made according to the ASTCT criteria (Lee et al., 2019).

Trial treatment should be permanently discontinued in case of a grade 4 CRS event or a cytokine blockade-refractory grade 3 CRS lasting >72 hours. However, per protocol, observation procedures and assessments are to continue until the subject withdraws from the trial or starts another course of systemic anticancer therapy.

Rescue medication, in terms of antidotes to reverse the action of GEN1053, are not available and potential events of CRS must be treated symptomatically. Subjects with CRS should receive supportive care following an international guideline (Lee et al., 2014) or local SoC, with supportive treatment controlling fever, hypotension, and hypoxia and in more severe cases with IL-6 mAb (tocilizumab), systemic steroids and vasopressors.

Infusion-Related Reactions Associated With GEN1053 Administration

The following treatment guidelines are provided below for subjects who experience an IRR associated with administration of trial treatment:

- Grade 1: If an IRR grade 1 occurs, the infusion does not need to be interrupted and can be continued at the investigator's discretion at half the infusion rate under close medical supervision.
- Grades 2 to 3: If an IRR grade 2 or 3 occurs, the infusion should be interrupted, and appropriate medical management instituted. The infusion may be restarted at the investigator's discretion at half the infusion rate under close medical supervision if symptoms have resolved to \leq grade 1 within an hour.
 - Subjects who have experienced prior infusion-related grade 2 or 3 reactions in the trial should be premedicated. Premedication to prevent IRR in subsequent infusions may be administered at the investigator's discretion according to local guidelines but preferably includes an antihistamine (eg, diphenhydramine 50 mg or equivalent antihistamine), acetaminophen/paracetamol (eg, acetaminophen 500-1000 mg or equivalent), and if considered necessary, subjects should receive corticosteroids at a suggested maximum dose of 100 mg prednisone or equivalent.
 - If the subject has a second grade 3 IRR despite premedication, the infusion should be stopped, and the subject should discontinue trial treatment.
- Grade 4: If anaphylaxis or grade 4 IRR occurs, trial treatment should be discontinued immediately and permanently, and appropriate medical therapy should be administered.

Note:

- As a routine precaution, all subjects must be observed during Cycle 1 and Cycle 2 on Day 1 for at least 4 hours after ending infusion of GEN1053. For all subsequent cycles, subjects must be observed for at least 2 hours after ending infusion of GEN1053, unless they have experienced an IRR in any previous cycle. In the latter case, the clinical observation should continue to be 4 hours. Subjects must always be observed for at least 2 hours after ending infusion of IM.
- During dose escalation, an overnight stay will be required for the first subject in each DL and may be required for additional subjects if recommended by the sponsor.
- Subjects must be observed in an area with resuscitation equipment and emergency agents.
- At all times during infusion of trial treatment, immediate emergency treatment of an anaphylactic reaction according to institutional standards must be assured. In order to treat possible anaphylactic reactions, for instance, dexamethasone 10 mg and epinephrine in a 1:1000 dilution or equivalents should always be available along with equipment for assisted ventilation.
- All premedications must be reported on the concomitant medication page in the eCRF.

6.7.2.4 Safety Stopping Rules for Trial Treatment

Treatment with trial treatment should be discontinued due to safety concerns under the following conditions:

- Subjects experiencing a DLT (refer to Section 6.7.1) should discontinue trial drug immediately. If requested by the investigator, the sponsor may allow a subject with a DLT to continue in the trial. For this decision, a thorough benefit-risk assessment of the individual subject is required, and consultation of the DMC may be considered.
- If a subject experiences a toxicity that would have qualified as a DLT, but that occurs after the DLT evaluation period, the subject's benefit-risk must be thoroughly assessed. Continued treatment with GEN1053 and/or IM must be agreed between the sponsor and the investigator.
- If the subject experiences a TRAE that meets the criteria for treatment discontinuation as specified in Sections 6.7.2.2 and 6.7.2.3 and Table 6-3 and Table 6-4.
- An AE that fails to resolve to \leq grade 1 within 21 days due to a toxicity possibly related to trial drug, unless otherwise approved by the sponsor medical monitor.
- Treatment-related grade 4 or life-threatening AE, except with approval from the medical monitor.
- Second occurrence of an IRR of \geq grade 3 despite premedication prior to the second infusion.
- First occurrence of anaphylaxis or a grade 4 IRR.
- Subjects with grade 4 transaminase or bilirubin elevation.
- Subjects with abnormal liver function parameters that meet Hy's law criteria as defined in Section 6.7.1.
- In case of thrombocytopenia not resolving to ≤ grade 1 within 21 days after the planned dosing date, unless approved otherwise by the sponsor.
- If the subject experiences grade 4 thrombocytopenia or grade 3 thrombocytopenia with clinically significant bleeding.
- First episode of CRS grade 4.
- First episode of cytokine blockade-refractory grade 3 CRS lasting >72 hours.

Note:

• Subjects should, whenever possible, irrespective of the reason for discontinuation, be examined as soon as possible for details regarding discontinuation of treatment (refer to Section 7.1).

6.7.2.5 Safety Stopping Rules for the Trial

The trial can be stopped for unacceptable toxicity based on a risk-benefit assessment after consultation with the DMC. Deaths considered related to GEN1053 will always be assessed by the DMC.

In addition, trial stopping rules for unacceptable toxicity will be introduced in the Expansion part based on data collected during the Dose Escalation part of this trial.

6.8 Treatment of Overdose

6.8.1 Overdose of GEN1053

For this trial, an overdose of GEN1053 is defined as a subject receiving a dose in excess of 10% of that specified in this protocol.

In case of overdose, medication errors, misuse, and/or abuse of GEN1053, subjects should receive supportive care according to local guidelines and potential side effects of GEN1053 should be treated symptomatically.

In the event of an overdose, the investigator should:

- Closely monitor the subject for any AEs/SAEs and laboratory abnormalities.
- Obtain a plasma/serum sample for PK analysis if requested by the sponsor's medical monitor (determined on a case-by-case basis).
- Document the quantity of the excess dose as well as the duration of the overdose.
- Contact the sponsor's medical monitor immediately (see Section 8.4.3).

6.8.2 Overdose of IM

Further details on the IM will be provided in a substantial amendment before initiating phase 1b of the trial.

6.9 Treatment After the End of the Trial

6.9.1 Subject Contact and Trial Treatment After the End of the Trial

Investigators should attempt to recontact the subject to obtain long-term follow-up information regarding the subject's safety or survival status as noted in the ICF (refer to Appendix 1, Informed Consent Process).

For subjects with a potential treatment benefit, subjects may be eligible for continued treatment with Genmab IMP(s) by an extension protocol or as provided for by the local country's regulatory mechanism. However, Genmab reserves the unilateral right, at its sole discretion, to determine whether to supply Genmab IMP(s) and by what mechanism, after termination of the trial and before the product(s) is/are available commercially.

7 DISCONTINUATION OF TRIAL TREATMENT AND SUBJECT DISCONTINUATION/WITHDRAWAL

7.1 Discontinuation of Trial Treatment

Subjects can decline to continue receiving trial treatment and/or other protocol-required therapies or procedures at any time during the trial but continue participation in the trial. Subjects who have discontinued trial treatment and/or other protocol-required therapies or procedures should not be automatically removed from the trial. Whenever safe and feasible and unless the subject withdraws consent, it is imperative that subjects remain on-trial to ensure safety surveillance and/or collection of outcome data (ie, continue efficacy evaluations according to the trial protocol).

The subject may discontinue both trial treatment and further participation in trial activities; however, they may continue to be followed for survival (see Section 7.1.2) and are not considered discontinued from the trial (see Section 7.2), provided that consent for trial participation has not been withdrawn.

A subject's trial treatment must be discontinued for any of the following reasons:

- Unacceptable AE requiring treatment discontinuation (refer to Section 6.7.1 and 6.7.2.4)
- Pregnancy
- Clinical progression
- Radiographic PD or confirmed radiographic PD by iRECIST (if applicable) Note: If the investigator considers radiographic changes secondary to drug-induced inflammation and not to tumor progression, the investigator may postpone a diagnosis of PD until the next radiographic evaluation in the trial (see Section 8.2.4 for treatment beyond PD).
- Death
- Investigator believes that it is in the best interest of the subject to stop GEN1053 or GEN1053+IM treatment
- Subject non-compliance
- Sponsor decision
- Subject request to discontinue trial treatment
- Lost to follow-up (see Section 7.3)
- Termination of the trial by the sponsor

For subjects receiving GEN1053+IM combination therapy, both GEN1053 and IM should be discontinued. Subjects may only continue GEN1053 or IM monotherapy if approved by the sponsor.

Subjects should, whenever possible, irrespective of the reason for discontinuation, be examined as soon as possible and the treatment discontinuation visit should be performed. If the treatment discontinuation visit coincides with a regularly scheduled cycle visit, the treatment discontinuation evaluations will supersede those of the regularly scheduled cycle visit. If the timing of the treatment discontinuation visit and first safety follow-up visit are the same, the treatment discontinuation visit may represent the first safety follow-up visit. For subjects crossing over from GEN1053 to GEN1053+IM, re-baseline visit details are provided in Table 1-13.

When a subject discontinues treatment with trial treatment, the subject remains in the trial and is followed until meeting one of the reasons listed in Section 7.2.

In addition, the subject will still be followed for safety (see Section 7.1.1) and survival status (see Section 7.1.2) through the end of the trial.

Subjects should always be followed for safety as detailed in Section 8.4 and Appendix 3.

After trial treatment discontinuation, the subject should receive suitable treatment as decided by the investigator (see Section 6.9).

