8.2.3 Assessment of Disease Response and Progressive Disease

- On-trial imaging will be performed at Week 6 (-7 days), every 6 weeks (±7 days) for 50 weeks, and every 12 weeks (±7 days) thereafter from the date of first dose until PD is assessed by the investigator (unless the investigator elects to continue treatment and follow iRECIST beyond RECIST PD), the start of new anticancer therapy, withdrawal of consent, or death, whichever occurs first. Imaging assessments should follow calendar days and should not be adjusted for delays in cycle starts. If imaging shows PD, then a subsequent imaging assessment, in clinically stable subjects only, should be performed within 4 to 7 weeks to confirm PD if following iRECIST. Imaging is not required when subject is in survival follow-up.
- Imaging assessments should be scheduled using the date of first dose as the reference date (not the date of the previous tumor assessment) and should be respected regardless of whether trial treatment is temporarily withheld, or unscheduled assessments performed.
- The reading of the scans will be done by a local radiologist. To the greatest extent possible, sites should maintain the same radiologist throughout the trial. Results from the radiology

evaluations are to be recorded, and a copy of the evaluation reports should be kept in the subject's file. RECIST 1.1 criteria will be used for secondary endpoint response evaluation (Eisenhauer et al., 2009) and Appendix 7; iRECIST will be used for exploratory endpoint response evaluation (Seymour et al., 2017).

- Additional CT or MRI scans may be performed at the investigator's discretion to confirm response or new symptoms. Tumor imaging to confirm PR or CR should be performed at least 4 weeks after the first indication of a response is observed. In this case, the investigator must choose the imaging technology based on the clinical indication.
 - If an off-schedule imaging assessment is performed because progression is suspected, subsequent imaging assessments should be performed in accordance with the original imaging schedule.
 - Additional imaging assessments may be performed at any time during the trial at the investigator's discretion to support the efficacy evaluations for a subject, as necessary. Clinical suspicion of PD at any time requires a physical examination and imaging assessments to be performed promptly rather than waiting for the next scheduled imaging assessment.

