- Sites will be required to submit electronic copies of prebaseline scans (since failure of last prior therapy, as available) and all subsequent scans on an ongoing basis to a centralized imaging CRO for exploring the tumor growth and possible independent review of disease assessments for subjects enrolled. Images obtained at an unscheduled timepoint should be captured in the eCRF and submitted to the central imaging vendor for subjects enrolled in the Expansion part.
 - Imaging data will be centrally collected and checked for quality by an imaging CRO designated by the sponsor. The local investigator's assessment will be used as primary for the endpoint analyses and for treatment decision making. Central review of the imaging data may be performed if deemed necessary.

8.2.4 *iRECIST* Assessment of Disease

For subjects who continue trial treatment beyond initial RECIST-defined PD, efficacy assessments must continue.

iRECIST is based on RECIST 1.1 but has been modified to account for the unique response patterns observed with immunotherapy. In this trial, iRECIST will be evaluated as an exploratory endpoint (Seymour et al., 2017).

iRECIST PD should be confirmed within 4 to 7 weeks after the first radiologic evidence of PD in clinically stable subjects. Subjects who have unconfirmed PD may continue on-trial treatment until PD is confirmed as long as the subject is clinically stable and has provided written informed consent prior to receiving additional treatment. Subjects who are clinically stable must meet the following criteria:

- Subject must have clinical benefit from continuation of trial treatment (as assessed by the investigator) and must not have rapid PD
- Subject is tolerating trial treatment
- Subject must have a stable ECOG status
- Treatment beyond PD will not delay an imminent intervention to prevent serious complications for PD (eg, CNS metastases requiring immediate treatment).

Any clinically unstable subjects should be discontinued from trial treatment at the first occurrence of radiographic PD. Subjects that are clinically unstable are not required to have repeated imaging to confirm PD by iRECIST; however, a confirmation of progression scan may be obtained at the investigator's discretion after consultation with the sponsor.

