9.4.2 Efficacy

9.4.2.1 Antitumor Activity Based on RECIST 1.1

RECIST criteria (v1.1) will be used to define response (Eisenhauer et al., 2009). Additional details of RECIST can be found in Appendix 7.

The BOR is the best response recorded from the start of the treatment until PD/recurrence (the smallest measurements recorded will be used as the reference for PD). Subjects with CR or PR are considered to be objective responders. Subjects with CR, PR, or SD are considered to be in disease control. Subjects for whom data are NE are counted as nonresponders.

The best change (maximal reduction in the sum of the diameters in the target lesions) in target lesions at any time on trial will be reported using waterfall plots.

Individual subject data listings and summaries of objective response, best overall tumor response, and disease control will be presented by dose cohort/indication and total.

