9.4.2.1.1 Objective Response Rate

The confirmed ORR is defined as the proportion of subjects with BOR of confirmed CR or confirmed PR (ie, "responders"), as per local review and according to RECIST v1.1. Repeat imaging may be performed no less than 4 weeks after the criteria for CR or PR are met to confirm the initial response.

An assessment of SD requires at least 5 weeks from C1D1 to scan date.

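### Section 7.1 lets a diagnosis of PD be postponed to the next scan, and no rule says how that scan is recorded or dated for RECIST 1.1, so DCR, PFS and confirmed ORR can be biased favourably

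*Combined protocol and SAP*

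**What the plan says.** The Note in Section 7.1 sits under the radiographic-PD item of the list of reasons for stopping trial treatment. If the investigator attributes the changes to drug-induced inflammation and not to tumor progression, "the investigator may postpone a diagnosis of PD until the next radiographic evaluation in the trial". It then points to Section 8.2.4 for treatment beyond PD.

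Section 8.2.3 gives one reading two jobs: "The local investigator's assessment will be used as primary for the endpoint analyses and for treatment decision making". It also keeps two sets of criteria apart. "RECIST 1.1 criteria will be used for secondary endpoint response evaluation", while "iRECIST will be used for exploratory endpoint response evaluation". Central review is optional.

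The endpoint definitions all run to PD:

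- **BOR (9.4.2.1):** "The BOR is the best response recorded from the start of the treatment until PD/recurrence".
- **DCR (9.4.2.1):** CR, PR or SD. For SD, Section 9.4.2.1.1 says: "An assessment of SD requires at least 5 weeks from C1D1 to scan date".
- **DoR (9.4.2.1.2):** ends at first PD or death.
- **PFS (9.4.2.2.3):** ends at first documented PD or death, by local RECIST 1.1 review.

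Section 8.2.4 speaks of continuing treatment after an initial PD defined by RECIST, and lets clinically stable subjects with unconfirmed PD stay on treatment pending confirmation.

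Section 9.4.2.1 also says that the best change "in target lesions at any time on trial will be reported using waterfall plots". It gives no cut-off at PD or at crossover.

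**The concern.** What the Note allows to be postponed is the diagnosis, and the protocol does not separate the diagnosis used for treatment from the one used for endpoints. It does not say whether a postponed scan is recorded as PD, SD or NE. Nor does it say whether a PD shown at the following scan is dated back to the first.

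If a site enters the postponed scan as SD, RECIST 1.1 takes over part of what iRECIST is there to do, and the comparison between the two becomes blurred. ORR, DCR and DoR by RECIST 1.1 are the secondary efficacy endpoints. Confirmed ORR also drives the monitoring and success rules in Section 9.5. The trial is open-label with local reading, so a discretionary deferral can favour the drug.

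**Working it through.** **1. What one postponement can do under the text**

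- **DCR.** The first scan is at Week 6 (-7 days), that is, 5 to 6 weeks after C1D1, so it can satisfy the 5-week SD rule. With 40 subjects per cohort (Section 9.2), each first-scan PD entered as SD adds 1/40 = 2.5 percentage points. Two add 5 points and four add 10.
- **PFS.** Scans are every 6 weeks for 50 weeks, then every 12. One postponement moves the recorded event by one interval: 6 weeks, or 12 late in follow-up. A Week 6 event becomes a Week 12 event.
- **ORR.** BOR stops at PD. If PD is not recorded, BOR stays open and a later confirmed CR or PR counts. Nothing changes unless such a response follows.
- **DoR.** A responder whose PD is postponed has a longer DoR. Responders who exist only through deferral would also enter the DoR set, with durations that cannot be predicted. The direction for the cohort is therefore not fixed.

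**2. The plan's own figures**

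Section 9.2 states at least 90% power for 10% versus 30% with n = 40, one-sided 5%. The exact binomial rule is at least 8/40, with alpha 4.2% and power 94.5%, so the statement reproduces.

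Section 9.5 requires a posterior probability of at least 80% that ORR exceeds p0, with a Beta(p0, 1-p0) prior.

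- **HNSCC (p0 = 10%):** 5/40 gives 0.648 and 6/40 gives 0.807, so the count is 6.
- **NSCLC (p0 = 15%):** 8/40 gives 0.775 and 9/40 gives 0.877, so the count is 9.

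Both agree with Table 9-3.

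**3. Illustration for the success rule**

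The documents give no deferral rate. Let q be an assumed share of subjects who count as responders only because a PD was postponed. Ignoring interim looks,

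P(X ≥ r) = 1 − Σ (x = 0 to r−1) C(40, x) p^x (1−p)^(40−x), with p = p0 + q.

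| q (assumed) | Expected extra responders (40q) | HNSCC: P(X ≥ 6), p0 = 10% | NSCLC: P(X ≥ 9), p0 = 15% |
|---|---|---|---|
| 0 | 0 | 20.6% | 13.5% |
| 1 point | 0.4 | 27.4% | 18.0% |
| 2.5 points | 1 | 38.4% | 25.7% |
| 5 points | 2 | 56.7% | 40.7% |

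Table 9-3 states 17% (HNSCC) and 10% (NSCLC) at these base rates, lower than the first row because it includes futility looks. Applying the HNSCC look printed in the table (at least 2/20), the HNSCC column becomes 19.3%, 25.7%, 36.3% and 54.2%. The pattern does not depend on leaving the looks out.

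**4. The passages side by side**

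If RECIST PD is always recorded first, as 8.2.3 and 8.2.4 imply, the wording of 7.1 contradicts them. If 7.1 is taken literally, the RECIST 1.1 endpoints contain deferred PD and overlap with iRECIST. No passage chooses between the two.

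**The case against.** The strongest reply is that the Note is only a treatment rule. It stands in a discontinuation list, refers to treatment beyond PD, and is cited by none of the endpoint definitions. Sections 8.2.3 and 8.2.4 presuppose that RECIST PD is recorded before iRECIST takes over. This may well be the intention, and it is why the endpoints cannot be said to be inflated. It does not remove the ambiguity, because 8.2.3 uses one reading for both purposes and sites could follow either text.

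Second, a footnote in Appendix 7 discounts findings thought to be something other than tumor, so some deferrals fit RECIST 1.1. That stands, although the copy reviewed does not show which criterion the footnote belongs to. It contains no rule for waiting until the next scan. The target-lesion limb of PD is a measured one: at least 20% and at least 5 mm growth from nadir.

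Third, the stakes are limited. The primary endpoints are safety endpoints, there is no confirmatory testing (9.1), the futility thresholds are nonbinding (9.5), PFS is exploratory, and the SAP is still to be finalized. All of this stands and keeps the point at the level of a clarification that should be made.

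A reader might also infer that waterfall plots for Cohort 1 will include scans taken on GEN1053+IM. The text does not say so. Section 7.1 mentions a re-baseline visit at crossover, Table 1-13 is still a placeholder, and Section 9 treats crossover data as possible exploratory analyses. What stands is that no cut-off is stated.

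**Conclusion.** The concern holds as a conflict between 7.1 and Sections 8.2.3 and 8.2.4 with no rule to resolve it. Following the literal text can bias DCR, PFS and confirmed ORR, and for these three any effect is favourable. If the postponed scan is recorded as NE, or a later PD is dated back, DCR and PFS do not gain.

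The size cannot be derived. The 2.5 DCR points and the 6- or 12-week shift are per affected subject. The 27.4% to 56.7% range against 20.6% rests wholly on the assumed 1 to 5 points.

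Three stronger readings are not supported:

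- **That the endpoints are inflated.** The documents show only that they can be.
- **That DoR is lengthened for the cohort.** Its direction is not fixed.
- **That the chance of success at a true ORR of 10% rises from 20.6% to 37.1%.** The arithmetic is right, since P(X ≥ 5) = 37.1%, but it presumes one deferral-created responder in every cohort of 40, and nothing in the documents supports that.

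**What to change.** 1. In Sections 8.2.3 and 9.4.2, state that for BOR, ORR, DCR, DoR and PFS, RECIST 1.1 PD is recorded and dated at the first scan that meets Appendix 7, including its footnote on non-tumor findings, whatever the treatment decision. Deferred cases are captured as iUPD and enter the iRECIST endpoints only.
2. Reconcile the Note in 7.1 with 8.2.3 and 8.2.4 so that the three agree on recording. No treatment rule needs to change.
3. In Section 9.4.2.1, limit best change in the waterfall plot to scans up to first RECIST PD and, in Cohort 1, before the first GEN1053+IM dose.

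The cost is protocol wording and eCRF guidance, with no change to imaging or to patient care. DCR and PFS may come out slightly less favourable. With the rule in place, the deferral terms in the working are zero and do not disturb the planned operating characteristics.
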